3.3. Secondary Study Endpoints

The secondary endpoints of the study will be change in peripheral blood absolute neutrophil count (ANC) in cells $\times 10^9/L$ [Δ (postWSP (4 hr) – preWSP)[γ T] vs Δ (postWSP (4 hr) – preWSP)[placebo]] and [Δ (postWSP (24 hr) – preWSP)[γ T] vs Δ (postWSP (24 hr) – preWSP)[placebo]].

Exploratory endpoints of interest include:

1. Role of asthma as a modifier of γ T treatment effect on WSP-induced airway inflammation
2. Spirometry measurements – forced vital capacity (FVC), forced expiratory volume in 1 second (FEV₁), FEV₁/FVC ratio
3. Secretion of sputum mucins (total sputum mucins, MUC5AC, MUC5B) will be determined by Western blot
4. Serum cytokine concentrations via Mesoscale:
 - a. TH1 cytokines: IL-1b, IL-6, IL-8, TNFa
5. Sputum cytokine concentrations via Mesoscale:
 - a. TH1 cytokines: IL-1b, IL-6, IL-8, TNFa
6. Flow mediated dilation (FMD) using brachial artery ultrasound
7. Left ventricular strain (LVS)
8. Serum concentrations of gT aT gCEHC and aCEHC.

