6.2. Statistical Methods

Our analytic plan was developed in collaboration with [name], the biostatistician for the CEMALB, who will oversee all statistical analysis. For analysis of sputum and circulating PMN responses as well as cytokine changes within each treatment group, we will use (i) descriptive analysis, (ii) two-sample comparison test, and (iii) random effects regression analysis (Equation 1) designed to take advantage of the crossover design (22). Specifically, we will use the tabular and graphic methods to describe/explore the basic relationship between the groups. We will then follow up by comparing the Δ sputum %PMNs (post WSP – pre WSP [γ T]) vs (post WSP – pre WSP [placebo]) using two-sample tests, either parametric (T-Test) or nonparametric (Wilcoxon signed-rank test), depending on whether the normality assumption is met. We will transform the data to achieve normality if needed. Finally, we will employ a random effect regression modeling technique (Equation 1) that allows us to assess treatment effect while accounting for potential period effect and carry-over effects. This approach is similar to those we have previously described to assess genotype effects (including the GSTM1 null genotype) on response to pollutants (11, 23-25) and is shown below. In all analyses, criterion for significance will be $p \leq 0.05$. To address potential missing data, we will employ multiple imputation methods to address this issue when appropriate; using techniques we have previously described (24).

Linear mixed model approach for global unified analysis of data for secondary and exploratory outcomes:

$$Y_{11k} = \mu + \pi_1 + \tau_1 + \beta X_k + s_{1k} + \epsilon_{11k}; Y_{12k} = \mu + \pi_2 + \tau_2 + \lambda_1 + \beta X_k + s_{1k} + \epsilon_{12k}$$

$$Y_{21k} = \mu + \pi_1 + \tau_2 + \beta X_k + s_{2k} + \epsilon_{21k}; Y_{22k} = \mu + \pi_2 + \tau_1 + \lambda_2 + \beta X_k + s_{2k} + \epsilon_{22k}$$

μ is the grand mean, π_1 and π_2 are period effects, τ_1 and τ_2 are treatment effects, λ_1 and λ_2 are carryover effects for different sequences, s_{1k} and s_{2k} are individual random effects within each sequence, and ϵ 's are random errors. Subscript k is for subjects.

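### Equation 1's unconstrained carryover terms reduce its treatment estimate to the period 1 between-subject difference, which hits hardest the exploratory outcomes that have no other named test

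*Combined protocol and SAP*

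**What the plan says.** Section 6.2 lists three analysis steps: description, a two-sample comparison, and a "random effects regression analysis (Equation 1) designed to take advantage of the crossover design". It gives the model's aim as a technique "that allows us to assess treatment effect while accounting for potential period effect and carry-over effects".

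The four displayed cell equations contain two period effects, two treatment effects, a covariate term βX_k, a random subject effect within sequence, and λ1 and λ2, which "are carryover effects for different sequences". λ1 appears only in period 2 of sequence 1 and λ2 only in period 2 of sequence 2. Nothing constrains them, no rule drops them, and X_k is not defined.

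The equations stand under the heading "Linear mixed model approach for global unified analysis of data for secondary and exploratory outcomes". The section's opening sentence names the outcomes that receive all three steps: "For analysis of sputum and circulating PMN responses as well as cytokine changes within each treatment group, we will use" description, the two-sample test and the regression. Section 3.3 makes blood absolute neutrophil count (ANC) the secondary endpoint. Its exploratory list also includes spirometry, sputum mucins, flow mediated dilation (FMD), left ventricular strain (LVS) and serum tocopherols, none of which section 6.2 assigns to the two-sample test. On the threshold the section says "In all analyses, criterion for significance will be" p ≤ 0.05.

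**The concern.** In a two-by-two crossover there are four sequence-by-period cell means. A grand mean, a period effect, a treatment effect and a free carryover difference use up all four. Once each period 2 cell has its own carryover term, period 2 says nothing about treatment. What remains is a parallel-group comparison of period 1, although the model is meant to exploit the crossover.

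The consequence differs by outcome:

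- **Spirometry, mucins, FMD, LVS, tocopherols:** Equation 1 is the only named analysis, so the within-subject comparison is lost and real effects are more likely to be missed.
- **ANC and cytokines:** two analyses of different precision are planned at the same threshold, with no statement of which governs if they disagree.
- **Sputum %PMN (primary):** only the follow-up model is affected, provided the first-line test is paired. The Wilcoxon signed-rank option is paired; the text does not say whether the t-test is.

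**Working it through.** **The plan's own figure.** Section 6.1 gives an effect of 14.5 with SD 25.9, α = 0.05, 80% power and n = 28. Take 25.9 as the SD of the within-subject difference and a two-sided test (the text states neither). Then n = (25.9 × (1.960 + 0.842) / 14.5)² = 25.04, so 26. The exact paired t-test has power 79.96% at 27 and 81.5% at 28, so 28 reproduces as a within-subject figure. A parallel two-sample test with that SD would need 51 per group.

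**What Equation 1 estimates.** Without X_k, the expected cell means are:

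- sequence 1: μ + π1 + τ1, then μ + π2 + τ2 + λ1
- sequence 2: μ + π1 + τ2, then μ + π2 + τ1 + λ2

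With λ1 and λ2 free, the two period 2 means are fitted exactly whatever τ1 − τ2 is. The design matrix has rank 4. Generalised least squares gives τ1 − τ2 the weights (1, 0, −1, 0) on cells (seq 1 p1, seq 1 p2, seq 2 p1, seq 2 p2) at every correlation tried. Setting λ1 = λ2, or using a sequence term instead of the λ terms, gives (½, −½, −½, ½), the within-subject contrast.

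A simulated mixed-model fit with 14 per sequence agreed. With a carryover term the estimate was −23.526, identical to the raw period 1 difference, with standard error 8.90; without it the standard error was 3.57. Deleting some period 2 values left −23.526 unchanged. Deleting some period 1 values let the random effect recover a little information (−23.92 against a raw difference of −23.26).

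**Size.** Let σ² be the per-period variance and ρ the between-period correlation, with 14 subjects per sequence.

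- Equation 1: variance = 2σ²/14 = 0.1429σ².
- Within-subject: variance = σ²(1 − ρ)/14.
- Ratio = 2/(1 − ρ); matching N = 28 × 2/(1 − ρ).

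The documents give no ρ, so a range is assumed.

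| | ρ = 0 | 0.3 | 0.5 | 0.7 |
|---|---|---|---|---|
| Within-subject variance (σ²) | 0.0714 | 0.0500 | 0.0357 | 0.0214 |
| Variance ratio | 2.00 | 2.86 | 4.00 | 6.67 |
| Interval width ratio | 1.41 | 1.69 | 2.00 | 2.58 |
| N under Equation 1 to match 28 | 56 | 80 | 112 | 187 |
| Interval ratio, 35 start (18 + 17), 7 leave after period 1 (4 + 3) | 1.33 | 1.57 | 1.84 | 2.35 |
| Power under Equation 1 where within-subject power is 80% (t, 26 df) | 51% | 38% | 29% | 19% |

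**The price of dropping λ.** The within-subject contrast has expectation τ1 − τ2 + (λ2 − λ1)/2. Its mean squared error is the smaller unless |λ1 − λ2| exceeds 2√(2/14 − (1 − ρ)/14) = 2√((1 + ρ)/14) per-period SDs, that is 0.53, 0.61, 0.65 and 0.70 at the four values of ρ.

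**The case against.** Five points can be made for the plan as written.

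1. **X_k may recover some precision.** Suitable baselines exist: spirometry and blood measures at V0, FMD and LVS at V1. If X_k is a baseline correlated ρ with each period, the variance ratio becomes 2(1 + ρ). Intervals are then 1.41, 1.61, 1.73 and 1.84 times as wide, and power is 51%, 41%, 37% and 33%. This stands: the upper end of the table is the case without X_k. X_k is undefined, however, and the within-subject comparison is still lost.

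2. **The model protects against carryover bias.** The text states two aims, and free λ terms serve one of them. The sequence model fits the same four cell means and differs only in calling the fourth degree of freedom sequence rather than carryover. This also stands: the choice trades variance for bias, and the plan does not acknowledge it.

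3. **The sputum planning values do not establish the size.** With SD 25.9 and ρ = 0.5 the standard error goes from 25.9/√28 = 4.89 to 9.79. With the screening responders' SD of 13, the period 1 standard error is 13 × √(2/14) = 4.91, no real loss. The two SDs come from different settings and together imply ρ = 1 − 25.9²/(2 × 13²) ≈ −0.98. I therefore rest nothing on that illustration.

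4. **The stakes are limited.** The outcomes with no other test are all exploratory and carry no stated power. For tocopherol levels the loss may not matter, since section 1.1 reports clear rises in the earlier trials. Both are fair.

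5. **The heading already points to Equation 1 for ANC.** It does, but the opening sentence adds a second test at the same threshold and the text never ranks them.

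**Conclusion.** The point holds. As written, Equation 1 gives period 2 no weight in the treatment estimate. This follows from the algebra whatever the correlation. It is exact when period 1 is complete, including when subjects drop out after period 1, and nearly so when some period 1 values are missing. Imputing missing period 2 values would not change their zero weight.

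The size rests on compound symmetry, about 14 completers per sequence and an assumed ρ. Even at ρ = 0 the variance doubles. Over 0 to 0.7, intervals are 1.4 to 2.6 times as wide without X_k and 1.4 to 1.8 times with a baseline as X_k. No stated power is contradicted, because the plan gives none for these outcomes. This should be fixed before analysis; it does not undermine the first-line primary test if that test is paired.

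**What to change.** - Replace the main Equation 1 model with fixed treatment, period and sequence effects and a random subject intercept, without λ1 and λ2. Name the covariates in X_k or delete the term.
- For ANC and cytokines, state that this within-subject estimate governs and that the two-sample test, run paired, is supportive.
- State that the model assumes no differential carryover and rests on the washout.
- Report the sequence (carryover) contrast, or the model with λ terms, only as a labelled sensitivity result. It must not choose the estimator.
- As a descriptive check, in subjects who took γT first, compare pre-exposure γT at V5 (when they are on placebo) with V0. Both samples are already scheduled (sections 5.1.2 and 5.1.4).

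The cost is wording only, with no new visit or sample. The downside is real: true differential carryover would bias the new estimate by half of λ1 − λ2 in size, and a two-by-two design cannot separate it from a sequence effect. Protection comes from the nominal 4 to 8 week washout (section 5.1.6) plus 1 to 3 weeks from V4 to V5 (section 5.1.5), longer where the postponements in section 5.1.7 apply. The documents do not show that this is enough, and the V5 check detects residual plasma γT only, not other forms of carryover.

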6.3. Data Management

Study coordinators will be responsible for efforts and computations for database management. Data will be initially collected by study coordinators on paper documents. Clinical data such as health history will be collected by study staff as interview or directly measured, such as vital signs, spirometry, etc. All paper forms (source documentation) are maintained by a study coordinator or PI in a binder, 1 binder per subject. All data will be entered into REDCap by a study coordinator within 2 weeks of collection, and will be verified by a 2nd person within 4 weeks to ensure accuracy and completeness. REDCap is a secure web application developed at Vanderbilt University and can be used to collect virtually any type of data (including 21 CFR Part 11, FISMA, and HIPAA-compliant environments). It is specifically geared to support online or offline data capture for research studies and operations. Missing data will be noted and a comment made in the database to explain the missing data. Time stamps will be used when appropriate. At minimum, the visit number will be indicated.

Biological samples collected by coordinators will be delivered to the CEMALB lab by the coordinators in properly labeled containers. On receipt in the lab, samples are initially entered into a software program called LDMS (Lab Data Management System) which tracks samples. Processing of these samples is done per the SOP maintained in the CEMALB quality assurance plan, as some samples are processed immediately and others are processed in batches at later time points. This data is entered into REDCap at appropriate intervals, based on sample analysis.

We will use the data dictionary or REDCap codebook as our course for data codes. All data will be collected by qualified staff using CEMALB SOPs and will be entered into REDCap. Once the data is entered and confirmed by a 2nd person, it will be considered “locked” and will not be changed without documentation with the reason for the change. REDCap limits and monitors who can change data, a feature developed to ensure data integrity.

6.4. Randomization plan

The randomization schedule will be generated by [name] (biostatistician) and provided to the investigational pharmacy. Only [name] and the pharmacist will have access to the randomization schedule. Subjects will be allocated to begin the first period of the crossover study with placebo or γ T treatment using permuted block randomization with a block size of 4 (2 placebo, 2 γ T for the first treatment period of the protocol).

7. Monitoring and Risk Minimization

7.1. Definition of Adverse Event (AE) and Serious Adverse Event (SAE)

Adverse events and serious adverse events will be recorded and reported according to 21 CFR 312.32. An adverse event for a given volunteer will be defined as any untoward medical occurrence associated with the use of a drug whether or not considered drug related and will also include failure of any of the safety criteria outlined in section “3.4.”. Additionally, minor upper respiratory tract infections occurring within 96 hours of the exposure will be considered adverse events. Other non-specified clinical illnesses or symptoms, which occur during the treatment period or within 96 hours of each challenge, will also be reported as an AE. Any decrease in lung function or increase in symptom score, as outlined in section “3.4,” will be considered an

adverse event. Any symptoms that induce a volunteer to seek medical attention from any provider during study drug treatment or within 7 days of completing study drug treatment or within 96 hours of challenge will be considered an adverse event. A serious adverse event will also be defined as any event that requires hospitalization or results in life threatening illness or injury, permanent (or likely to be permanent) illness or injury, or death if these events occur during study drug treatment or within 7 days of completing study drug treatment or within 96 hours of challenge (or if the clinical scenario leading up to hospitalization, illness, injury or death begins during study drug treatment, within 7 days of completing study drug treatment or within 96 hours of a challenge).

7.1.1. Grading criteria

In addition to determining whether an adverse event fulfills criteria for a serious adverse event or not, the severity of adverse events experienced by study participants will be graded according to the criteria set forth in the Toxicity Grading Scale for Healthy Adult and Adolescent Volunteers Enrolled in Preventive Vaccine Clinical Trials except for those items listed in 7.1.2 below. This document provides a common language to describe levels of severity, to analyze and interpret data, and to articulate the clinical significance of all adverse events.

All adverse events whether or not listed in the Toxicity Grading Scale will be graded on a scale from 1 to 4 according to the following standards (A semi-colon indicates 'or' within the description of the grade.):

Grade 1 = Mild; asymptomatic or mild symptoms; clinical or diagnostic observations only; intervention not indicated.

Grade 2 = Moderate; minimal, local or noninvasive intervention indicated; limiting age-appropriate instrumental ADL (preparing meals, shopping for groceries or clothes, using the telephone, managing money, etc).

Grade 3 = Severe or medically significant but not immediately life-threatening; hospitalization or prolongation of hospitalization indicated; disabling; limiting self care ADL (bathing, dressing and undressing, feeding self, using the toilet, taking medications, and not bedridden).

Grade 4 = Life-threatening consequences; or urgent intervention indicated.

7.1.2. Protocol specific potential AE's

Adverse events which have relative specificity for this protocol will be recorded and graded 1 to 4 according to the grade definition provided below:

	Mild (Grade 1)	Moderate (Grade 2)	Severe (Grade 3)	Potentially life-threatening (Grade 4)
Gastrointestinal distress (i.e. diarrhea, nausea, vomiting, flatulence)	Asymptomatic or mild symptoms; clinical or diagnostic observations only;	Moderate; minimal, local or noninvasive intervention indicated; limiting age appropriate	Severe or medically significant but not immediately life-threatening; hospitalization or prolongation of	Life-threatening consequences; urgent intervention indicated

	intervention not indicated	instrumental ADL	existing hospitalization; disabling; limiting self care ADL	
Coagulopathy with or without bleeding	Asymptomatic or mild symptoms; clinical or diagnostic observations only; intervention not indicated	Moderate; minimal, local or noninvasive intervention indicated; limiting age appropriate instrumental ADL	Severe or medically significant but not immediately life-threatening; hospitalization or prolongation of existing hospitalization; disabling; limiting self care ADL	Life-threatening consequences; urgent intervention indicated

7.2. Risks to Subjects

7.2.1. Potential risks of gamma tocopherol

There is a rare chance that higher doses of α T may effect coagulation (PT and aPTT) and predispose to bleeding. It is possible that γ T carries the same risk, though this has not been demonstrated in prior studies of γ T. An observational study of un-supplemented individuals suggested that higher plasma γ T levels were associated with reduced lung function, specifically FVC and FEV₁ (14). Finally, our prior studies with γ T have demonstrated risk for mild gastrointestinal symptoms, including diarrhea, nausea, bloating, and flatulence that tended to occur early on during treatment and to self-resolve within a few days despite continued treatment. In our most recent randomized, placebo controlled crossover study evaluating 14 days of γ T supplementation in adults with asthma, diarrhea was reported in 26% of subjects on active treatment, compared to 4.3% of subjects on placebo.

7.2.2. Potential risks of WSP

Concentrations of wood smoke exhaust proposed for this study (500 μ g/m³) are below those reported for individuals using biomass burning for heating and food preparation and those living in the area of a forest fire or agricultural burning. No major adverse health effects were observed in a recently completed study which exposed healthy volunteers to concentrated Chapel Hill air particles at the EPA Human Studies facility (Physiological and Biochemical Changes Associated with Exposure to Air Pollution Particles; [name], PI; IRB# 95-EPA-310)1. The mean particulate matter (PM) was $485 + 84 \mu\text{g}/\text{m}^3$ during the WSP exposure (vs. "below the detectable limit" for filtered air (FA)), and analyses of chamber concentrations of total hydrocarbon and carbon monoxide during WSP exposure were also increased compared to FA (4.8 ± 0.5 vs. 2.0 ± 0.1 ppm and 2.7 ± 0.7 vs. 0.0 ± 0.0 ppm, respectively). However, these healthy subjects had no significant change in pulmonary function and no nasal irritation, rhinitis, inspiratory pain,

shortness of breath, cough, wheezing or chest tightness after exposure to WSP or filtered air. There were complaints of fatigue, headache and eye irritation, but these were noted by volunteers as frequently before as after both the filtered air and particle exposures. Pulmonary function testing demonstrated no significant changes from pre-exposure values following exposures to either filtered air or WSP.

There is potential for increased airway inflammation in asthmatics. Thus, we are limiting inclusion to mild asthmatics only. Seven participants with asthma have completed an ongoing screening protocol (UNC IRB approved study #15-1775, *To identify persons who are susceptible to WSP-induced inflammation and examine the role of GSTM1 and other factors in this susceptibility*) to identify mild asthmatics who experience a $\geq 10\%$ increase in sputum neutrophilia after WSP exposure for inclusion into this study. In addition to the mild, transient symptoms experienced by healthy volunteers as noted above, these seven asthmatic participants have experienced transient chest tightness following WSP exposure. This symptom has not been accompanied by any significant changes in spirometry, and chest tightness has resolved spontaneously within a few minutes following exposure and without any intervention. We will assess for any symptoms following WSP exposure with the WSP exposure questionnaire immediately after exit from the chamber and again 4 hours later. Spirometry will also be performed immediately following exit from the chamber with additional spirometry to be performed for any persistent symptoms and/or physician discretion. If FEV1 drops by 20% or more immediately after wood smoke exposure, or if the subject has intolerable symptoms, albuterol will be given for rescue. Finally, our Center has previously performed inhaled challenges with ozone and LPS in the allergic asthmatic population. With ozone and LPS we have not experienced any serious adverse events, and we expect the response to the wood smoke challenge to be similar.

7.2.3. Potential Risks of the Induced Sputum Procedure

The saline solutions (3%, 4% and 5%) nebulized during sputum may cause throat irritation, but it is uncommon for the duration of discomfort to last more than a few minutes post procedure. The procedure also has a minimal risk of inducing bronchospasm, which is a potential concern for individuals with asthma. Thus, all volunteers with a history of asthma will be pre-treated with 2-4 puffs of albuterol prior to beginning sputum induction. Additional albuterol is employed as a rescue agent if needed, and a physician is available for all sputum induction procedures.

7.2.4. Potential Risks of Spirometry

Potential risks include possible lightheadedness or wheezing.

The adhesive patches used during monitoring may cause itching or skin irritation.

